2. RATIONALE, OBJECTIVES, AND BENEFIT - RISK ASSESSMENT

2.1 RATIONALE FOR PERFORMING THE TRIAL

Psoriasis is a chronic inflammatory disease affecting 2% of the world population with significant impact on patient quality of life and associated with significant systemic disease. IL-23 plays a key role in the pathophysiology of psoriasis through induction and maintenance of Th-17 type cells that secrete inflammatory cytokines. BI 655066 is a humanized monoclonal antibody that specifically neutralizes the IL-23 axis. Proof of clinical concept (PoCC) for BI 655066 was demonstrated in a single dose phase I trial in 39 patients with moderate to severe plaque psoriasis where 87% of patients achieved at least 75% reduction in Psoriasis Area and Severity Index (PASI 75) with no safety concerns (1311.1, [c02434648](#)).

The current trial is being performed to assess the safety and efficacy of BI 655066 to support registration for the treatment of moderate to severe chronic plaque psoriasis in adult patients.

2.2 TRIAL OBJECTIVES

The main objectives of this study are to assess the efficacy and safety of BI 655066 compared to adalimumab in patients with moderate to severe chronic plaque psoriasis. The primary efficacy evaluation will be performed at 16 weeks and an assessment of maintenance of response will be performed at 44 weeks. The study will also evaluate the efficacy of a 28 week treatment with BI 655066 in patients who were initially treated with adalimumab for 16 weeks, achieving insufficient or only partial response with adalimumab, and then switched to BI 655066 treatment from Week 16 to Week 44.

In addition, this trial will assess PK and the emergence of anti-drug antibodies (ADA) and their effect on efficacy and safety. Moreover, it will be explored how the use of BI 655066 may influence gene and protein expression levels and disease specific protein markers.

Lastly, the influence of study treatment on some metabolic risk factors will be looked into.

2.3 BENEFIT - RISK ASSESSMENT

Participation in this study may help to generate future benefit for larger groups of patients with psoriasis if BI 655066 proves to be successful in treating this disease. BI 655066 has been studied in approximately 200 patients with moderate to severe plaque psoriasis. In these studies, the majority of patients receiving BI 655066 achieved 90% improvement of their disease. The most common adverse events reported in these trials were mild symptoms of the upper respiratory tract, including nasal stuffiness, sore throat, and influenza, and headache, that showed no dose dependency. These events were not considered to be related to drug treatment. Local reactions following subcutaneous administration of BI 655066 were uncommon, and limited to redness, swelling or induration at the injection site. No serious drug related adverse events were reported.

As with many immune modulating agents, BI 655066 may impair immune function resulting in a risk of infection. This will be monitored by collection of all AEs during the treatment and observation periods. Patients with clinically important active infection will not be included in the study.

There is not enough information at this time to rule out a risk of cancer with BI 655066, but this risk is considered small with this type of compound as experience with the anti-IL 12/23 mAb ustekinumab has not suggested significant risk for cancer/serious infection.

Increases in major adverse cardiovascular events (MACE) including myocardial infarction, cerebrovascular accident, and cardiovascular death, reported initially with anti-IL-12/23 agents, such as ustekinumab, have not been observed in longer term studies. While the likelihood of increased MACE is small, all suspected cardiovascular events, serious or non-serious, observed in this study will be adjudicated by an independent MACE Adjudication Committee.

All patients will receive active treatment in this study, either BI 655066 or adalimumab; there is no placebo comparator in this trial. Adalimumab (Humira[®]) is used as an established treatment for patients with moderate to severe psoriasis and has been on the market in many countries for many years. Adalimumab has an acceptable safety profile.

Although rare, a potential for drug-induced liver injury is under constant surveillance by sponsors and regulators. Therefore, this trial requires timely detection, evaluation, and follow-up of laboratory alterations in selected liver laboratory parameters to ensure patients' safety, see also [Section 5.3.6.1](#).

In order to recognize any safety signals as early as possible, an independent Data Monitoring Committee (DMC) will monitor this study and all studies where patients are receiving BI 655066.

In conclusion, the benefit-risk profile is considered appropriate for this stage of clinical development.

3. DESCRIPTION OF DESIGN AND TRIAL POPULATION

3.1 OVERALL TRIAL DESIGN AND PLAN

This confirmatory multi-national, randomized, double-blind, double dummy, active controlled, parallel design study compares BI 655066 with adalimumab. In total, approximately 600 patients with moderate to severe chronic plaque psoriasis will be randomized in this trial.

Patients are included in the study once they have signed the informed consent. Patients suitable after screening will be eligible to participate in the 44 week treatment period and will be randomized at a ratio of 1:1 to one of 2 treatment arms (BI 655066 or adalimumab) shown in [Figure 3.1: 1](#).

Patients initially randomized to BI 655066 will stay on BI 655066.

At Week 16, patients initially on adalimumab and <PASI 50 will be switched to BI 655066.

At Week 16, patients initially on adalimumab and \geq PASI 90 will stay on adalimumab.

At Week 16, patients initially on adalimumab and \geq PASI 50 and <PASI 90 will be re-randomised 1:1 to receive either BI 655066 or adalimumab.

[figure not shown]

Figure 3.1: 1 Trial design

Patients will be blinded to treatment. Patients in each dose group will receive the same injections (active or placebo) at each designated time point, in order to maintain blinding.

Patients starting and continuing with BI 655066 active drug will receive 2 syringes of BI 655066 active drug (2 x 75mg) at randomization, at Weeks 4, 16 and 28 and placebo adalimumab at randomization (2 syringes) and 1 placebo adalimumab syringe at Weeks 1, 3, 5, 7, 9, etc. up to Week 41. These patients also receive 2 syringes of BI 655066 placebo at Weeks 20 and 32 to maintain blinding to the BI 655066 active treatment arm starting at Week 16 after adalimumab pre-treatment. BI 655066 active treatment always starts with a loading dose 4 weeks after the first injection.

Patients starting with active adalimumab and switching to active BI 655066 at Week 16 will receive 2 syringes active adalimumab at randomization (2 x 40mg) followed by 1 syringe active adalimumab (40mg) at Weeks 1, 3, 5, 7, 9, 11, 13, 15; and 1 placebo adalimumab syringe at Weeks 17, 19, 21, etc. up to Week 41 to maintain blinding. These patients also receive 2 syringes of BI 655066 placebo at randomization and Week 4 followed by two active BI 655066 injections (2 x 75mg) at Weeks 16, 20 and 32 as well as 2 placebo BI 655066 injections at Week 28.

Patients starting and continuing with adalimumab active drug will receive 2 syringes active adalimumab at randomization (2 x 40mg) followed by 1 syringe active adalimumab (40mg) at Weeks 1, 3, 5, 7, 9, etc. up to Week 41. These patients also receive 2 syringes of placebo BI 655066 at randomization and at Weeks 4, 16, 20, 28 and 32.

Individual patient participation is concluded when the patient has completed the last planned visit. The “last-patient-last-visit-primary-endpoint” is the last scheduled primary endpoint visit at Week 16 completed by the last patient. The end of the trial is defined as “last patient out”, i.e. last scheduled visit completed by last patient.

Patients will be offered to roll over into an open label extension (OLE) trial if they have completed the study 1311.30 and meet the inclusion criteria for the OLE trial.

Patients who terminate the study drug early in study 1311.30, will complete EOT Visit procedures instead of the planned treatment period visit and return 16 (± 1) weeks after the last BI 655066 (active or placebo) administration for EOO Visit. Discontinuation of study medication should not necessarily lead to withdrawal from the study. If possible, the patient should be further followed up and complete all study visits and procedures until EOO.

Patients who complete the randomized treatment period of study 1311.30, but will not be included in the OLE study will have their EOO Visit 4 (± 1) weeks after their EOT Visit at Week 44 (which is at Week 48 ± 1 week).

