16. Study personnel completes a questionnaire about self-administration of BI 655066 (active or placebo) by the patient (refer to [section 4.1.4](#), [5.6.2](#) and [Appendix 10.8](#))
17. Adalimumab (active or placebo) is dispensed to the patient for self-administration at home (at Weeks 5, 7, 9, 11, 13, 15, 17, 19, 21, 23, 25, 27, 29, 31, 33, 35, 37, 39 and 41). Time window for home administration should be \pm 3 days.
18. Patients who complete the randomized treatment period of study 1311.30 will be offered to roll over into an open label extension (OLE) trial if they fulfill the in- and exclusion criteria for the OLE trial. Those patients will have no Follow-up Visit in study 1311.30.
Patients who discontinue the randomized treatment period of study 1311.30 prematurely will complete EOT Visit procedures and return 16 (\pm 1) weeks after their last BI 655066 (active or placebo) administration for End of Observation (EOO) Visit.
Patients who complete the randomized treatment period of study 1311.30, but will not (or cannot) be included in the OLE study will have their EOO Visit 4 (\pm 1) weeks after their EOT Visit at Week 44 (this is at Week 48 \pm 1 week).
19. For randomised patients who will not participate in the OLE study and who withdraw from the study prior to their planned EOO Visit, vital status should be collected at 48 (+1) weeks after the Randomisation Visit.
20. Patients that terminate trial medication early should remain in the trial if possible, and complete all remaining study visit procedures if possible. Termination of trial medication should be completed in the e CRF and treatment discontinuation registered in IRT. Refer to [Section 6.2.3](#) for more details

TABLE OF CONTENTS

CLINICAL TRIAL PROTOCOL	1
TITLE PAGE	1
CLINICAL TRIAL PROTOCOL SYNOPSIS	2
FLOW CHART	6
TABLE OF CONTENTS	9
ABBREVIATIONS	13
1. INTRODUCTION.....	16
1.1 MEDICAL BACKGROUND.....	16
1.2 DRUG PROFILE	16
2. RATIONALE, OBJECTIVES, AND BENEFIT - RISK ASSESSMENT	18
2.1 RATIONALE FOR PERFORMING THE TRIAL	18
2.2 TRIAL OBJECTIVES.....	18
2.3 BENEFIT - RISK ASSESSMENT.....	18
3. DESCRIPTION OF DESIGN AND TRIAL POPULATION.....	20
3.1 OVERALL TRIAL DESIGN AND PLAN	20
3.1.1 Administrative structure of the trial	21
3.1.2 Data Monitoring Committee (DMC).....	22
3.1.3 MACE Adjudication Committee	22
3.2 DISCUSSION OF TRIAL DESIGN, INCLUDING THE CHOICE OF CONTROL GROUP	23
3.3 SELECTION OF TRIAL POPULATION	23
3.3.1 Main diagnosis for trial entry	23
3.3.2 Inclusion criteria	23

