3.3.4 Removal of patients from therapy or assessments

3.3.4.1 Removal of individual patients

All patients have the right to withdraw from the study at any time without the need to justify their decision. The investigator has the right to remove patients from the study for non-compliance, administrative or other reasons. It should be clearly understood that an excessive rate of withdrawals can render the study results uninterpretable. The sponsor reserves the right to remove any study patient from the trial for non-compliance.

An individual patient is to be withdrawn from trial treatment if:

- The patient withdraws consent for study treatment or study participation, without the need to justify the decision.
- The patient can no longer be treated with trial medication for other medical reasons (such as surgery, adverse events, other diseases, or pregnancy)
- Development of a toxicity or adverse event which warrants BI 655066 discontinuation including but not limited to SAEs or SUSARs
- If prohibited treatment is used during the study for any indication, the subject must discontinue use of the prohibited treatment if he/she wishes to continue in the study. In case of undue safety risk for the subject, the subject should discontinue study treatment at the discretion of the investigator. If the subject received a live virus vaccination during the study, the subject must discontinue study treatment.

- If the patient experiences an intolerable increase of psoriasis during the course of the trial the patient will be discontinued from the trial to receive treatment as deemed appropriate by the investigator.

Of note: Discontinuation of study medication should not necessarily lead to withdrawal from the study. If possible the patient should be further followed up and complete all study visits and procedures as initially planned.

Given the patient's agreement, the patient will undergo the procedures for early treatment discontinuation and follow up as outlined in the [flow chart](#) and [section 6.2.3](#).

Patients who discontinue the trial after receiving the first dose of study medication at Visit 2 will not be replaced.

For randomised patients leaving the study before the planned EOO, vital status should be collected at the date of the planned EOO Visit for a completed patient not going into the OLE study. Vital status assessment for discontinued patients should occur at 48 (± 1) weeks after randomisation.

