6.2.3.1 Early treatment and trial termination

If study medication is discontinued prior to the planned [Flow Chart](#) visit EOT, every effort should be made to have the patient continue in the trial and complete all of the remaining trial visits and procedures including EOT and EOO Visit; with the EOO Visit to be performed 4 weeks after the EOT Visit.

If a patient cannot or will not continue in the trial, the patient should complete EOT Visit procedures instead of the next planned treatment period visit. These patients should be registered as prematurely discontinued in IRT and return to the clinic for End of Observation Visit 16 (± 1) weeks after their last administered dose of BI 655066 (active or placebo). Patients who discontinue from the trial prematurely will not have the option to participate in the open label extension (OLE) study.

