7.5 HANDLING OF MISSING DATA

Every effort should be made to collect complete data at all visits.

The following rules will be used to impute for missing data:

- For all non-binary endpoints, LOCF (Last Observation Carried Forward) will be used to impute missing values
- For all binary endpoints (i.e. endpoints that are either 1 (patient responded) or 0 (patient did not respond)):
 - If no data after that visit*, then impute as failure (NRI [No Response Imputation])
 - If data at visits* before and after, only impute as success if both visits are successes; else impute as failure.

* Patients that take prohibited medications to treat psoriasis will be treated the same as those that discontinued from the trial – i.e. subsequent visits following start of prohibited medication will be considered as failure for binary endpoints.

Missing items from the Quality of Life questionnaires will be handled according to the measure instructions (cf. [Appendix 10.6](#) and [10.7](#)). If there is no data for a particular visit, then it will be imputed following the same rules as described above.

Sensitivity analyses to assess the robustness of the hypothesis testing results will include:

- LOCF (for binary endpoints)
- Logistic regression
- MMRM (for continuous endpoints)
- Multiple imputation (for binary endpoints)

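### Protocol Section 3.1 sends every patient who stops study drug down the path that Section 6.2.3.1 keeps for patients leaving the trial; read literally, some re-randomised patients who stay would have no Week 44 PASI

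*Protocol*

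**What the plan says.** Two parts of the current protocol text set a visit path for patients who stop study drug.

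- **Section 3.1.** "Patients who terminate the study drug early in study 1311.30, will complete EOT Visit procedures instead of the planned treatment period visit". They return for EOO 16 (±1) weeks after the last BI 655066 (active or placebo) injection. The paragraph adds that stopping drug need not mean withdrawal, and continues: "If possible, the patient should be further followed up and complete all study visits and procedures until EOO". The only EOO it defines for these patients is the 16-week one. The Week 48 EOO in the next paragraph is for patients who complete the treatment period.
- **Section 6.2.3.1.** This section separates two groups. Patients who stop drug but stay are to "complete all of the remaining trial visits and procedures including EOT and EOO Visit; with the EOO Visit to be performed 4 weeks after" EOT. The 16-week path has a condition: "If a patient cannot or will not continue in the trial, the patient should complete EOT Visit procedures".

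Three other places bear on this.

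- **Section 3.3.4.1** sides with 6.2.3.1: "If possible the patient should be further followed up and complete all study visits and procedures as initially planned". It refers the reader to the Flow Chart and Section 6.2.3.
- **Flow Chart footnote 20** does the same: "Patients that terminate trial medication early should remain in the trial if possible, and complete all remaining study visit procedures if possible". It also refers to Section 6.2.3.
- **Flow Chart footnote 18** gives the 16-week EOO as follows: "Patients who discontinue the randomized treatment period of study 1311.30 prematurely will complete EOT Visit procedures". It does not say whether this means stopping drug or leaving the trial.

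The Flow Chart schedules PASI/sPGA at EOT but not at EOO. For a missing binary outcome, Protocol Section 7.5 says: "If no data after that visit*, then impute as failure". SAP Section 10.1.4 applies the same non-responder rule.

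**The concern.** The same patient gets different EOT and EOO dates depending on which section the site opens. Under Section 6.2.3.1, a patient who stops drug and stays has a PASI at Week 44, and the observed value counts. Under a literal Section 3.1, the patient has an early EOT, reaches EOO some weeks later and is then finished. With nothing observed at or after Week 44, the patient is scored a failure.

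The endpoint at stake is Week 44 PASI 90 in the re-randomised patients. It has its own test at 0.05 (Protocol Section 7.2), it sets the requirement for 300 adalimumab patients (Section 7.7), and the SAP makes it the Part B primary endpoint (Section 10.2). With about 70 sites planned (Section 3.3), the instruction should be the same wherever it is read.

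**Working it through.** **1. The plan's own figure.** Protocol Section 7.7 gives 56 per arm for 90% power at 70% v 40%. The check uses two-sided 0.05, pooled variance under the null and no continuity correction. The mean rate is 0.55.

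n = [1.96·√(2·0.55·0.45) + 1.2816·√(0.70·0.30 + 0.40·0.60)]² / 0.30² = (1.379 + 0.860)² / 0.09 = 55.7, so 56. This matches.

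At the planned 60 per arm, power = Φ[(0.30 − 1.96·√(2·0.55·0.45/60)) / √(0.45/60)] = Φ[(0.30 − 0.178)/0.0866] = Φ(1.41) = 0.92. This matches the stated figure of more than 90%.

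**2. When the literal Section 3.1 path ends.** BI 655066 or its placebo is injected at Weeks 0, 4, 16, 20, 28 and 32 in every arm (Protocol Section 4.1.4). EOO week = last injection week + 16 (±1). Part B day = (week − 16)·7 + 1. The SAP Week 44 window is Part B Days 184 to 211 (Section 6.0, Table 8).

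| Last injection | EOO under 3.1 | Part B day | Week 44 PASI if the patient stays |
|---|---|---|---|
| Week 4 (re-randomised, not dosed in Part B) | Week 20 | 29 | none |
| Week 16 | Week 32 | 113 | none |
| Week 20 | Week 36 | 141 | none |
| Week 28 | Week 44 | 197 | ambiguous: EOO falls in the window but has no scheduled PASI |
| Week 32 | Week 48 | 225 | not affected |

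The Week 4 row matters because the SAP provides for subjects re-randomised but not dosed in Part B (Table 8 note) and keeps them in ITT_B_RR (Section 5.1). The early EOT does carry a PASI, but for the first three rows it would normally fall before Day 184. Under Section 6.2.3.1, every row gives EOT with PASI at Week 44 and EOO at Week 48.

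**3. Illustrative size.** The documents give no stopping rate, so these inputs are assumptions:

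- stopping is equal in both arms and spread evenly over the 28 weeks of Part B;
- every stopper stays in the trial;
- every site concerned follows Section 3.1 literally;
- stoppers would otherwise respond at the planned rate for their arm.

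Stopping before the Week 28 injection covers 12/28 of the period. Adding patients whose last injection is at Week 28 makes it 16/28. Affected share a = stopping rate × 12/28 (or 16/28). Each arm's rate becomes p(1 − a), and the difference becomes 30(1 − a) points.

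| Stopping | Share used | a | Affected of 60 per arm | Difference (points) | Power |
|---|---|---|---|---|---|
| 0% | – | 0 | 0 | 30.0 | 0.920 |
| 2% | 12/28 | 0.86% | 0.5 | 29.7 | 0.915 |
| 5% | 12/28 | 2.14% | 1.3 | 29.4 | 0.907 |
| 10% | 12/28 | 4.29% | 2.6 | 28.7 | 0.893 |
| 2% | 16/28 | 1.14% | 0.7 | 29.7 | 0.914 |
| 5% | 16/28 | 2.86% | 1.7 | 29.1 | 0.903 |
| 10% | 16/28 | 5.71% | 3.4 | 28.3 | 0.883 |

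At 5% stopping with 12/28, the responders lost are 60 × 0.02143 × 0.70 = 0.9 on BI 655066 and 60 × 0.02143 × 0.40 = 0.5 on adalimumab. If only half the stoppers stay, a halves; at 10% stopping with 12/28 the result is then 1.3 of 60 and power 0.907.

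**The case against.** The strongest reply is that Section 3.1 is an overview, that Section 6.2.3.1 is the operative text, and that Section 3.3.4.1 and footnote 20 both send the reader to Section 6.2.3. The Section 3.1 paragraph itself asks for all study visits. The Flow Chart puts EOO after Week 44, so reading EOO there as a cut-off at Week 32 or 36 empties that request of much of its meaning. This stands as to intent, and it is why many sites would do the right thing. It does not remove the conflict. The Flow Chart's EOO timing carries footnote 18, and the only EOO that the Section 3.1 paragraph gives these patients is the 16-week one.

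A reader might infer that footnote 18 is a second, equal fault. The Flow Chart does not support that. It attaches footnote 18 to trial completion and EOO timing, and footnote 20 to termination of trial medication, so it already separates leaving the trial from stopping drug.

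A reader might also infer that failure imputation favours BI 655066. With equal stopping it shrinks the difference. With unequal stopping the direction depends on which arm loses more scores, and the documents do not say. LOCF and multiple imputation are listed as sensitivity analyses and could use the early-EOT PASI, but they would replace a Week 44 score that the rest of the protocol intends to collect.

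**Conclusion.** The conflict is in the current text and should be corrected, but its effect is small. It concerns only re-randomised patients who stop study drug, stay in the trial, had their last BI 655066 (active or placebo) injection at Week 4, 16 or 20 (Week 28 being ambiguous), and attend a site that follows Section 3.1 literally.

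Three groups fail at Week 44 on either path:

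- patients who leave with no later data, including those discontinued for an intolerable increase of psoriasis (Protocol Section 4.2.1);
- patients who take prohibited psoriasis medication before then (Section 7.5);
- patients who discontinue for worsening disease (SAP Section 10.1.4).

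Removing them lowers the figures.

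The size cannot be derived from the documents. With 2% to 10% stopping, about 0.5 to 2.6 of 60 per arm are affected, and power is 0.915 to 0.893. Including Week 28 stoppers gives 0.7 to 3.4 of 60 and 0.914 to 0.883. These are illustrations and should not be read as bounds: even stopping over time is an assumption, and patients re-randomised but never dosed in Part B are not counted separately.

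Two stronger readings are not supported. One is that the Week 16 co-primary analysis is compromised. A last injection at Week 4 puts EOO at Week 20, after that endpoint, and only a patient injected on Day 1 alone has an EOO that coincides with Week 16. The other is that the Week 44 sample size is wrong; it reproduces exactly and does not depend on this point.

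**What to change.** In Section 3.1, limit the sentence on early EOT and the 16-week EOO to patients who cannot or will not continue in the trial. Then state that patients who stop study drug but stay follow Section 6.2.3.1: all remaining visits, EOT with PASI/sPGA at Week 44, and EOO 4 weeks later. The same clarification in footnote 18 is optional. No PASI/sPGA needs to be added at EOO.

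The cost is a wording change in one paragraph. It adds no visit, assessment or analysis, and it asks of these patients only what Sections 3.3.4.1 and 6.2.3.1 already ask.
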